9.2.2. Study population

Inclusion criteria:

- Patient has two or more documented clinical visits in the National Anti-Tumor Drug Surveillance System (NATDSS) network on or after January 1, 2013.
- Patient has a confirmed diagnosis of DDLPS during his/her lifetime.
- At least 18 years old at the date of initial diagnosis

No exclusion criteria are applied.

Eligible population will be divided into two groups:

NIS Protocol BI Study Number 1403-0024

Page 13 of 37 C42272174

Proprietary confidential information© 2023 Boehringer Ingelheim GmbH or one or more of its affiliated companies

- Cohort 1 will include unresectable locally advanced or metastatic DDLPS patients who received at least one line of systemic antineoplastic treatment by the end of cohort identification period (index date = start date of 1L treatment).
- Cohort 2 will include patients with DDLPS who have not initiated 1L systemic antineoplastic treatment by the end of cohort identification period (index date = date of initial DDLPS diagnosis during cohort identification period). Patients initiated 1L treatment afterwards or patients received adjuvant and/or neoadjuvant therapy only through follow-up will be included in Cohort 2.

In both cohorts, 1L therapy will be defined as the initial set of drugs used after unresectable locally advanced or metastatic diagnosis. Metastatic patients will be defined as those with metastatic diagnosis or presence of metastatic sites; unresectable locally advanced patients will be defined as those with advanced diagnosis and without subsequent surgical resection.

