9.2.3. Study visits

Definitions of relevant time periods are detailed below.

Study period: January 1, 2013 – December 31, 2022

Baseline period: All available data prior to index date

[figure not shown]
Cohort identification period: January 1, 2013 – December 31, 2021 (one year before end of study period)

Index date: The index date for Cohort 1 will set to the date of initiation of 1L treatment; the index date for Cohort 2 will be the date of initial DDLPS diagnosis during cohort identification period.

Follow-up period: From index date until date of death, if available, or the date of censoring if there is no record of death, whichever occurs first. For survival and treatment patterns, the date of censoring will be the last activity date, defined as the date of the last visit of any type prior to the end of the study period.

Figure 1 illustrates the time periods for the study timelines.

(a). Cohort 1

NIS Protocol BI Study Number 1403-0024

Page 14 of 37 C42272174

Proprietary confidential information© 2023 Boehringer Ingelheim GmbH or one or more of its affiliated companies (b). Cohort 2

[figure not shown]

Figure 1. Overall study period

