10.1 MAIN ANALYSIS

10.1.1 Analysis of primary objective

OS will be analyzed for Cohort 1. For OS calculation, the event time is the date of death recorded by the National Mortality Database from CDC. OS is defined as the time from initiation of 1L until the date of death due to any cause. Patients without death record during the study period will be censored at the last medical record during the study period.

OS will be estimated by the KM method to obtain median estimates with 95% CIs and IQRs for Cohort 1, calculated using the log-log transformation. OS rate at 6, 12, 18, and 24 months will be described according to the survival curves if reached.

OS may be assessed by LOT and type of treatment received in each LOT, pending feasibility. OS by LOT is defined as the time from initiation of each LOT until the date of death due to any cause.

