10.1.2 Analysis of secondary objectives

Survival after initial diagnosis will be estimated by the KM method to obtain median estimates with 95% CIs and IORs for Cohort 1 and Cohort 2.

Treatment patterns for Cohort 1 and Cohort 2 will be described by the number of lines, count with percentage (%) of patients by treatment lines, type of therapy and therapy regimens in each line.

LOTs are defined by the temporal relationship and sequencing of treatment regimens by using the dates of initiation and discontinuation of chemotherapy, targeted therapy, and/or immunotherapy. For each patient, 1L treatment regimen is defined as the first systemic treatment of any chemotherapy, and/or targeted drugs given to a patient after advanced or metastatic DDLPS diagnosis. A treatment line is advanced to the next line when a patient initiates new combinations of drugs or has the evidence of progression of disease. The start date of each LOT is defined as the date of initiation of new regimen, and the end date of each LOT is defined as the date of last dose prescribed or recorded at/before discontinuation.

Statistical and Epidemiological Analysis Plan (SEAP) for Observational and Non-Interventional Studies (ONIS)

Page 18 of 36

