ANNEX 2. MOCK TABLE AND FIGURE

The following figures and tables will be developed for analyses of primary, secondary and exploratory objectives and will be replicated for subgroup analyses and sensitivity analyses, pending feasibility.

Table 1. Patient baseline demographic characteristics for Cohort 1 and Cohort 2

Demographic characteristics	Cohort 1	Cohort 2
Number of patients, N		
Index year, N (%) 2013		
2014		
2015		
2016		
2017		
2018		
2019		
2020		
2021		
Age at initial diagnosis, years		
$Mean \pm SD$		
Median (IQR)		
Min, Max		
Missing / Unknown		
Age (categorized) at initial diagnosis, N (%)		
<65		
≥65		
Missing / Unknown		
Age at index, years		
$Mean \pm SD$		
Median (IQR)		
Min, Max		

Statistical and Epidemiological Analysis Plan (SEAP) for Observational and Non-Interventional Studies (ONIS)

Page 21 of 36

Demographic characteristics	Cohort 1	Cohort 2
Missing / Unknown		
Age (categorized) at index, N (%)		
<65		
≥65		
Missing / Unknown		
Sex, N (%)		
Female		
Male		
Missing / Unknown		
Insurance type, N (%)		
National medical insurance		
Commercial insurance		
Out of pocket		
Others		
Missing / Unknown		
Region, N (%)		
Eastern China		
Central China		
Western China		
Northeast China		
Missing / Unknown		

Abbreviations: N = number; SD = standard deviation; IQR = interquartile range; min = minimum; max = maximum

Notes: Eastern China includes Beijing, Tianjin, Hebei, Shanghai, Jiangsu, Zhejiang, Fujian, Shandong, Guangdong, and Hainan; central China includes Shanxi, Anhui, Jiangxi, Henan, Hubei, and Hunan; western China includes Inner Mongolia, Guangxi, Chongqing, Sichuan, Guizhou, Yunnan, Tibet, Shaanxi, Gansu, Qinghai, Ningxia, and Xinjiang; northeast China includes Liaoning, Jilin, and Heilongjiang.

Statistical and Epidemiological Analysis Plan (SEAP) for Observational and Non-Interventional Studies (ONIS)

Page 22 of 36

Table 2. Patient clinical characteristics for Cohort 1 and Cohort 2

Clinical characteristics	Cohort 1	Cohort 2
Number of patients, N Year of initial diagnosis, N (%)		
Before 2013		
2013		
2014		
2015		
2016		
2017		
2018		
2019		
2020		
2021		
Missing / Unknown		
Disease stage at initial diagnosis, N (%)		
0		
I		
II		
III		
IV		
Missing / Unknown		
Histology, N (%)		
Dedifferentiated		
Other		
Missing / Unknown		
ECOG performance status, N (%)		
0		
1		
2		
3		
4		
Missing / Unknown		

Statistical and Epidemiological Analysis Plan (SEAP) for Observational and Non-Interventional Studies (ONIS)

Page 23 of 36

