Clinical characteristics	Cohort 1	Cohort 2
Primary tumor site, N (%)		
Head or neck		
Retroperitoneum or abdomen		
Extremity		
Pelvis		
Thorax or trunk		
Other		
Missing / Unknown		
Presence of metastases, N (%)		
Yes		
No		
Missing / Unknown		
Metastatic site, N (%)		
Adrenal		
Bone		
Brain		
Distant lymph node metastases		
Liver		
Lung		
Other		
Missing / Unknown		
Number of surgeries prior to 1L		
$Mean \pm SD$		
Median (IQR)		
Min, Max		
Missing / Unknown		
Charlson comorbidity index		
$Mean \pm SD$		
Median (IQR)		
Min, Max		
Missing / Unknown		
History of smoking, N (%)		

Statistical and Epidemiological Analysis Plan (SEAP) for Observational and Non-Interventional Studies (ONIS)

Page 24 of 36

Clinical characteristics	Cohort 1	Cohort 2
Never smoker		
Former smoker		
Current smoker		
Missing / Unknown		
$BMI, kg/m^2$		
$Mean \pm SD$		
Median (IQR)		
Min, Max		
Missing / Unknown		

Abbreviations: N = number; SD = standard deviation; IQR = interquartile range; min = minimum; max = maximum; BMI = body mass index (defined as [weight in kilograms] / [height in meters]²); ECOG = Eastern Cooperative Oncology Group; 1L = first line.

Statistical and Epidemiological Analysis Plan (SEAP) for Observational and Non-Interventional Studies (ONIS)

Page 25 of 36

Table 3. Overall survival from index for Cohort 1

At 18 months, [95% CI]

At 24 months, [95% CI]

	Cohort 1	
	N=	
Overall survival from Index, months		
KM Median, [95% CI]		
IQR		
Survival rate at different time point, (100/1000 person years) At 6 months, [95% CI]		
At 12 months, [95% CI]		

Abbreviations: KM= Kaplan–Meier; CI = confidence interval; IQR = interquartile range.

Statistical and Epidemiological Analysis Plan (SEAP) for Observational and Non-Interventional Studies (ONIS)

Page 26 of 36

Table 4. Survival from initial diagnosis for Cohort 1 and Cohort 2

	Cohort 1,	Cohort 2,	
	N =	N=	
Survival from initial diagnosis, months			
KM Median, [95% CI]			
IQR			
Survival rate at different time point, (100/1000 person years) At 6 months, [95% CI]			
At 12 months, [95% CI]			
At 18 months, [95% CI]			
At 24 months, [95% CI]			

Abbreviations: KM= Kaplan–Meier; CI = confidence interval; IQR = interquartile range.

Statistical and Epidemiological Analysis Plan (SEAP) for Observational and Non-Interventional Studies (ONIS)

Page 27 of 36

Table 5.	Number	of total	lines of	f systemic	treatment

	Cohort 1,	Cohort 2,
	N=	N=
Total lines of systemic treatment		
$Mean \pm SD$		
Median (IQR)		
Min, Max		

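### Non-metastatic patients stay in Cohort 1 only if no surgery follows, although OS starts at 1L; the effect on median OS is untested and of unknown size, and the two 1L definitions conflict for these patients

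*Protocol*

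**What the plan says.** - **Who counts as unresectable.** Protocol 9.2.2, repeated in SAP 6.3: "unresectable locally advanced patients will be defined as those with advanced diagnosis and without subsequent surgical resection". Metastatic status rests on a diagnosis or on recorded sites, whatever surgery was done. Neither definition carries a visible time limit or is tied to the start of 1L.
- **Time zero.** The Cohort 1 index date is the start of 1L (Protocol 9.2.3). SAP 10.1.1: "OS is defined as the time from initiation of 1L until the date of death due to any cause". Cohort identification closes on 31 December 2021, "one year before end of study period".
- **What 1L is.** Protocol 9.2.2 and SAP 6.3: "1L therapy will be defined as the initial set of drugs used after unresectable locally advanced or metastatic diagnosis". SAP 10.1.2 instead describes the first chemotherapy and/or "targeted drugs given to a patient after advanced or metastatic DDLPS diagnosis", without the condition of unresectability.
- **Cohort 2.** It takes patients with no 1L by the end of identification, and "patients received adjuvant and/or neoadjuvant therapy only through follow-up will be included in Cohort 2". Section 9.2.2 applies no exclusion criteria and splits the whole eligible population into two groups.
- **Checks.** Protocol 9.7.5 lists two sensitivity analyses, on mortality coverage and on the period before COVID-19. Protocol 9.9 does not mention the resection rule. Protocol 9.7.4 lists a locally advanced (LA) and a metastatic subgroup, both subject to sample size and feasibility.

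**The concern.** For a patient who never has metastases, membership of the primary population is decided after the survival clock has started. Removal by surgery after 1L start requires being alive at surgery. Among patients who might have been resected, early deaths stay in and those who reach surgery go out. This selection does not shrink as N grows, so the planned confidence interval cannot reveal it. It affects the Cohort 1 median and, more strongly, the LA subgroup median.

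The 1L wording is a second, separate problem. It affects the same patients and decides which cohort they enter and on what date their follow-up starts. Protocol 12 says the results may supplement regulatory submissions, so a reader should be able to see how many patients were moved by an event after time zero.

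**Working it through.** **1. The plan's own precision.** Protocol 9.5 gives 95% CIs for the median under exponential survival. A log-log interval for N=300 and median 8 gives (6.731, 9.351), against the stated (6.732, 9.435); with 20% uniform censoring it is (6.710, 9.438). The table therefore reproduces closely. At median 10 the stated half-widths are (10.784 − 9.262)/2 = 0.76 at N=1500 and (11.378 − 8.754)/2 = 1.31 at N=500.

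**2. Length of the look-ahead.** Data end on 31 December 2022. A patient starting 1L on 31 December 2021 can be observed for later surgery for 12 months; one starting on 1 January 2013, for up to 120 months.

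**3. Size of the selection.** The documents give no inputs for this, so all of these are assumed:
- true median 10 months, exponential, in patients who are not resection candidates (the target);
- LA share 30, 50 or 70%; candidates 10 or 20% of LA patients;
- candidates' survival time multiplied by m = 1, 1.5, 2 or 3;
- surgery uniform between 3 and 9 months after 1L, if alive.

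Let w be the candidates' share of the group analysed and p the proportion of candidates who die before surgery. With λ = ln2/(10m), p = 1 − (e^(−3λ) − e^(−9λ))/(6λ). The current rule keeps the non-candidates plus those early deaths. When the median falls after month 9 it equals 10 × [1 − log2(1 + wp/(1−w))].

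*Example:* LA 50%, candidates 20%, m = 2.
- w = 0.5 × 0.2 = 0.10; λ = 0.03466; p = 1 − (0.9013 − 0.7320)/0.2079 = 0.186.
- Current rule, Cohort 1: 10 × [1 − log2(1 + 0.0186/0.9)] = 9.70.
- Current rule, LA subgroup (w = 0.20): 10 × [1 − log2(1 + 0.0373/0.8)] = 9.34.
- Keeping later-resected patients, Cohort 1: solve 0.9x² + 0.1x = 0.5 with x = 2^(−t/20); x = 0.692, so t = 10.63.

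*All 24 combinations, shift from 10 months:*

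| | Current rule | Later-resected kept |
|---|---|---|
| Cohort 1 | −0.77 to −0.06 | 0 to +1.33 |
| LA subgroup | −1.16 to −0.20 | 0 to +1.99 |

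The current rule removes about 2 to 12% of otherwise eligible Cohort 1 patients (7 to 17% of LA). Only one of the 24 Cohort 1 shifts exceeds 0.76, and none exceeds 1.31. With true medians of 8 and 12 the Cohort 1 shifts are 0.05 to 0.7 and 0.06 to 0.8 months. With surgery at 1–4 or 6–12 months they are 0.02 to 0.4 or 0.08 to 0.9.

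**4. What can change the picture.**
- *Harmful resection.* Measured against a cohort that keeps later-resected patients (median 10, half never metastatic, 20% of those resected), the rule's effect shrinks to −0.12 months if resection doubles later hazard and becomes +0.22 if it triples it.
- *Re-entry.* If 40% of resected patients develop metastases and re-enter, the example gives 10.22 with 1L dated before surgery and 9.72 with 1L dated after metastasis.
- *Death capture.* Protocol 9.9 says that only 80% of deaths may be captured. Alone, that moves a median of 10 to about 12.0–12.5.

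**5. The 1L wordings side by side.** Take a patient with advanced, non-metastatic disease who receives systemic treatment and is then resected.
- Protocol 9.2.2 / SAP 6.3: never unresectable, so no 1L has started, so Cohort 2 with index at diagnosis.
- SAP 10.1.2: 1L has started, so not Cohort 2; resected, so not unresectable and not Cohort 1. The patient is in neither group.
- If metastases follow, 1L is the post-metastasis treatment under Protocol 9.2.2 / SAP 6.3 and the pre-surgery treatment under SAP 10.1.2: two possible index dates.

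The neoadjuvant-only sentence settles the case only where the treatment is identified as neoadjuvant.

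**The case against.** The strongest reply is that later surgery is evidence that the disease was resectable, so the current rule may be the better proxy for the population in the objective. This stands. Measured against non-candidates, the current rule is closer to the target than keeping later-resected patients in 12 of 12 combinations with m of 2 or 3. It is about equal at 1.5 and further away in 6 of 6 at 1. A reader might infer that the primary definition is wrong and should be replaced; the documents do not support that.

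Nor do they support reading the mechanism as a net under-estimate of OS. Incomplete death capture acts upward and is probably larger, and re-entry can reverse the sign. The two medians also do not bracket the truth: in the example with m = 0.7 both are low (9.31 and 9.64), and with re-entry and a pre-surgery index both are high (10.2 and 10.6).

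A larger effect, 0.2 to 2.8 months, appears if the yardstick is a cohort that keeps later-resected patients and up to 30% of LA patients are resected. That is a different target and should not be read as confirming the size.

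On the wording, SAP 6.3 repeats the protocol definition in full and SAP 10.1.2 may only be a shortened restatement. That makes the repair editorial, but the SAP still holds two definitions and does not say which governs.

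Two further points limit the concern without removing it. The metastatic subgroup is not defined by the resection rule, but it is optional and does not test the rule. Protocol 9.3.1.3, SAP pages 9–14 and the SAP text between 10.1.2 and 10.3 are not visible in the public copies, so an operational window there cannot be excluded.

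**Conclusion.** The concern holds in limited form. Membership of Cohort 1 and of the LA subgroup depends on an event after time zero that requires survival, and no visible analysis or limitation addresses it. For patients who stay non-metastatic, and if resection does not materially raise later hazard, the mechanism alone lowers the medians. At a true median of 10 months the Cohort 1 shift is about 0.1 to 0.8 months and the LA shift 0.2 to 1.2. The upper Cohort 1 figure comes from one corner of the grid (70% LA, 20% candidates, no survival advantage). These ranges rest wholly on assumed shares, surgery timing and survival ratios. The net direction for reported OS is not settled.

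The conflict between the 1L definitions rests on no numerical assumption and needs correction in any case. Together this is a missing sensitivity analysis and a wording conflict, worth fixing before analysis; it is not an error in the primary definition.

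**What to change.** 1. Reconcile the 1L wording of Protocol 9.2.2, SAP 6.3 and SAP 10.1.2, together with the neoadjuvant-only sentence, so that each such patient has one cohort and one index date, including when metastases follow.
2. Keep the primary definition. Report the number of otherwise eligible patients removed by resection after 1L start, and the time from 1L to resection.
3. Add to Protocol 9.7.5 and the SAP one OS sensitivity analysis, for Cohort 1 and the LA subgroup, that applies the resection rule only up to 1L start. State how treatment recorded as neoadjuvant is handled in it, since the Cohort 2 sentence would otherwise pull some of these patients back out. Present the result as a comparison that may overshoot, neither a bound on the true value nor a replacement for the primary estimate.
4. Add one sentence on this selection to Protocol 9.9. If text not visible here already sets a time window, cite it in 9.2.2.

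**Cost.** One extra Kaplan-Meier run for each of the two populations, a count with a time summary, one sentence and one wording alignment. The current rule already needs resection dates. SAP Annex 2 plans a row for "Number of surgeries prior to 1L", which requires ordering surgery against 1L, and says its tables and figures "will be replicated for subgroup analyses and sensitivity analyses, pending feasibility". The downside is that the extra estimate may include planned-neoadjuvant patients. SAP 9.4 sets a missing day to the 15th of the month, which will blur the before/after-1L ordering for some patients.

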9.2.3. Study visits

Definitions of relevant time periods are detailed below.

Study period: January 1, 2013 – December 31, 2022

Baseline period: All available data prior to index date

[figure not shown]
Cohort identification period: January 1, 2013 – December 31, 2021 (one year before end of study period)

Index date: The index date for Cohort 1 will set to the date of initiation of 1L treatment; the index date for Cohort 2 will be the date of initial DDLPS diagnosis during cohort identification period.

Follow-up period: From index date until date of death, if available, or the date of censoring if there is no record of death, whichever occurs first. For survival and treatment patterns, the date of censoring will be the last activity date, defined as the date of the last visit of any type prior to the end of the study period.

Figure 1 illustrates the time periods for the study timelines.

(a). Cohort 1

NIS Protocol BI Study Number 1403-0024

Page 14 of 37 C42272174

Proprietary confidential information© 2023 Boehringer Ingelheim GmbH or one or more of its affiliated companies (b). Cohort 2

[figure not shown]

Figure 1. Overall study period

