9.7.3. Analysis of exploratory objectives

Patient demographic, clinical characteristics and treatment outcomes will be reported for Cohort 1 and Cohort 2 (See Section 9.3.1.3 for variable definitions). If multiple records for a variable exist during the baseline period, the record closest to index will be chosen. The number of missing values will be reported for each variable, and percentages for categorical variables will be based on non-missing values. Time from diagnosis to 1L treatment, time to next treatment and duration of treatment by LOT will be estimated using KM methods to obtain median estimates with 95% CIs and IQRs.

HCRU including number of visits and days of hospitalization will be summarized as counts (n) and proportions (%). Direct medical cost will be summarized using mean, median and IQR.

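### The general baseline window stops before the index date, which in Cohort 2 is the day of DDLPS diagnosis, so tumour and performance-status variables with no timing of their own would omit records from that day and the work-up after it.

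*Protocol*

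**What the plan says.** Protocol 9.2.3 and SAP 6.4 carry the same time definitions. Baseline is defined once for both cohorts: "Baseline period: All available data prior to index date". The index dates differ. For the treated cohort, "The index date for Cohort 1 will set to the date of initiation of 1L treatment"; for the other, "the index date for Cohort 2 will be the date of initial DDLPS diagnosis during cohort identification period". Follow-up begins on the index date itself: "Follow-up period: From index date until date of death, if available".

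Protocol 9.7.3 reports demographic and clinical characteristics for both cohorts and adds a selection rule: "If multiple records for a variable exist during the baseline period, the record closest to index will be chosen". It bases percentages for categorical variables on non-missing values, as does SAP 10. Apart from partial dates, nothing is imputed (Protocol 9.7, SAP 9.4).

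For the variables themselves, Protocol 9.7.3 points elsewhere: "See Section 9.3.1.3 for variable definitions". That section is blacked out in the public text. The mock tables in SAP Annex 2 are visible. Table 2 ties one clinical variable to diagnosis by its label, "Disease stage at initial diagnosis, N". Others, such as "Primary tumor site, N", histology, ECOG, presence of metastases and metastatic site, have no timing in their labels.

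**The concern.** A baseline that ends the day before index works when the index event comes some time after the disease has been described. That is so in Cohort 1, where first-line treatment follows the advanced diagnosis. In Cohort 2 the index event is the diagnosis. The pathology result that confirms DDLPS, the imaging that locates the tumour and looks for spread, and the performance status noted at that visit are naturally dated on that day or soon after. A window that closes beforehand leaves out the records that best describe the patient at entry.

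At stake is the Cohort 2 column of SAP Table 2. Clinical characteristics are an exploratory objective but are named in the study title. If the rule is programmed as written, the percentages for the untimed variables would come from patients with a tumour or performance-status record older than their DDLPS diagnosis, for example those first seen for another or provisional diagnosis. If it is not programmed as written, the analyst has to choose a window that the plan does not give.

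**Working it through.** No sample-size or precision figure bears on this point. The check is date logic, with the passages set side by side.

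**Step 1. Windows.** Let D be the date of a record and I the index date. From Protocol 9.2.3 and SAP 6.4:

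- baseline: D < I
- follow-up: D ≥ I, up to death or censoring

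**Step 2. Index dates put in.**

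| Cohort | I | Record on the day of DDLPS diagnosis | Work-up just after diagnosis |
|---|---|---|---|
| 1 | start of first-line treatment, after the advanced diagnosis | normally baseline | baseline if before first-line start |
| 2 | date of initial DDLPS diagnosis | follow-up (D = I) | follow-up (D > I) |

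No visible text in either document adds the index day to baseline or opens a window around diagnosis.

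**Step 3. Which Cohort 2 variables depend on the general rule.**

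| SAP Table 2 row | Visible timing | Consequence in Cohort 2 |
|---|---|---|
| Year of initial diagnosis; disease stage | initial diagnosis | not affected |
| Histology | none | an earlier result can hardly be the one that confirmed DDLPS; it would fall under Other or be missing |
| ECOG | none | only values recorded before diagnosis count |
| Primary tumour site | none | only pre-diagnosis records count |
| Presence and site of metastases | none in Table 2; the definition in Protocol 9.2.2 is not limited to baseline | depends on which text the programmer follows |

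Histology shows the misfit most clearly but loses the least information, because inclusion already requires a confirmed DDLPS diagnosis.

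**Step 4. Effect on a reported percentage.** Let q be the share of Cohort 2 with a record of the variable before diagnosis. Let p_E be the proportion with the characteristic in that group and p_L the proportion among the rest. The table, using non-missing values, reports p_E. The whole cohort has q·p_E + (1 − q)·p_L. The difference is

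p_E − [q·p_E + (1 − q)·p_L] = (1 − q)(p_E − p_L).

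The distortion is zero if q = 1 or if the two groups are alike. It grows as fewer patients have early records and as those patients differ more from the rest. This treats an early record as correct; an outdated one adds a further error. The documents give neither q nor the two proportions, so no size can be stated.

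**Step 5. Does other visible text settle the index day?** It does not. The treatment-pattern table times first-line treatment type as after the index date, although in Cohort 1 that treatment starts on the index date and the outcome's own time frame includes the index date. Table 2 also asks for surgeries before first-line treatment in both cohorts, although Cohort 2 consists of patients who had not started it by the end of the identification period. Both suggest that the index day was not worked through separately for each cohort.

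**The case against.** The strongest reply is that the definitions that matter are hidden. Protocol 9.7.3 sends the reader to Section 9.3.1.3 for these variables, and the visible treatment-pattern table has a timing column for each variable, so the hidden table may have one too. Figure 1, which draws the Cohort 2 periods, is also not shown. Text withheld from the public version is not missing from the plan. This stands: nobody can say from the public text that the data will be missing. It does not remove the point, because the general definition is visible, is the same in both documents and does not fit Cohort 2. If Section 9.3.1.3 sets a different window, the two need to agree.

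Further replies also stand. The rule in Protocol 9.7.3 settles ties among baseline records and does not say that every characteristic must come from baseline. Tumour site, metastases and performance status can be recorded in work-up before the coded diagnosis date. Table 2 has a row for diagnoses before 2013; if such patients enter Cohort 2 through a first diagnosis record inside the identification period, their earlier data already cover the disease. Missing counts are to be reported for each variable, so a shortfall would be seen.

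A reader might infer that nearly all Cohort 2 patients would lack these variables, stage included. The documents do not support that: stage is labelled as at initial diagnosis, and nothing gives the share with earlier records. A reader might also infer that Cohort 1 has the same defect or that a comparison between cohorts is compromised. Cohort 1 is indexed after the advanced diagnosis, so earlier records should usually exist, and Protocol 9.3 plans no a priori comparison of groups.

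**Conclusion.** The point holds in a limited form. The general baseline window excludes the day of diagnosis in Cohort 2. Applied as written with the selection rule in Protocol 9.7.3, it leaves out diagnosis-day and early work-up records for histology, ECOG, primary site and metastases, and the percentages would then describe patients with earlier records. This is a stated rule that does not suit one of the two cohorts, and not merely an absent detail.

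The effect is confined to exploratory descriptive output for Cohort 2 and any subgroup repeats of it. Primary OS in Cohort 1 is untouched. The size cannot be derived. The conclusion rests on two assumptions: that the general definition is applied literally to variables without visible timing, and that Section 9.3.1.3 does not override it. If that section does override it, what remains is to bring Protocol 9.2.3 and SAP 6.4 into line with it.

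**What to change.** In Protocol 9.2.3 and SAP 6.4, redefine baseline as all available data up to and including the index date. For the Cohort 2 tumour and performance-status variables, state that the record closest to diagnosis is used, within a pre-specified window around it that ends at first treatment or surgery if that comes earlier. The sponsor should set and justify the window length before analysis, align it with any per-variable timing in Section 9.3.1.3, and state the timing in the row labels or a footnote of SAP Table 2. The selection rule in Protocol 9.7.3 should refer to the same window.

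The cost is a short wording change in two documents, with no new data. The downside is a brief post-index look-ahead for Cohort 2, which is acceptable for variables that only describe the cohort. A footnote should say so, and values taken after diagnosis should not be presented as if known before it.
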